Appendix XII – ShangRing Case Report Form: Client Follow-Up Form

CASE REPORT FORM – ShangRing DEVICE FOLLOW-UP

Evaluation of the safety and acceptability of the ShangRing device for male circumcision in Tanzania

Site Code:

Client ID # (CID):

INSTRUCTIONS FOR THE PROPER COMPLETION OF THE CRF

Please follow the instructions below:

1. This form is to be used for ALL follow-up visits, including the removal visit, and unscheduled visits.
2. Complete a new form at each follow-up visit.
3. Use a ball-pen, DO NOT use a pencil, a marker or a fountain pen.
4. Make sure to place the separator provided under the last copy of each page so that data recorded on one page does not copy to the next.
5. Subject initials will be comprised of the first letter of the first name followed by the first two letters of the surname.
6. Fill in the form in a clear, concise and readable way. Use common medical terminology.
7. Correct wrong data by crossing out the information with a single line and writing the correct data next to it. The evaluation coordinator, or the site coordinator in the evaluation coordinator's absence, will initial and date the correction.
 - a. Example: 07/03/1969 corrected to 09/03/1969 (with initials and date of the correction)
8. Complete all the available fields, DO NOT leave empty fields.
 - a. For evaluations not performed record ND (not done).
 - b. For data not relevant to the subject or stage of evaluation record NA (not applicable).
 - c. If you do not know the data, please use the initials UNK (unknown).
 - d. Use leading zeroes if necessary (e.g.: 15 mg = 0 1 5 mg).
 - e. Make sure to complete every header on each page.
9. Please make sure to **circle the correct option** whenever it is requested.
10. Please DO NOT add wording to CRF pages unless required. For any additional comments please use the Comments Sheet at the end of the CRF modules.
11. Dates (e.g., date of birth, date of visit) will be recorded in the DD/MM/YYYY format.
 - a. Example: 19 June 2017 will be recorded as 19/06/2017
12. CID is the Client Identification Number. It comprises the initials of the site followed by the four digit enrollment date and the three digit subject consecutive number. Example: Subject number 1 in Good Hope Health Center enrolled on July 21 will be GH2107001.
13. Time will be recorded in 24:00 format.

Example: 6:15 pm will be recorded as 18:15

ShangRing Client Follow-Up Form

Client ID Number: _____

Date of visit (dd-mm-yyyy): _____

Date of ShangRing Device Placement (dd-mm-yyyy): _____

Contact Type (select one):

- **On-site visit (specify name of facility/site):** _____
- **Off-site visit (specify location, i.e. work, home, school):** _____
- **Phone contact (number called):** _____

Type of Visit (select one):

- Removal visit (specify days since device placement): _____
- Day 42 post-placement healing assessment (specify day if client comes in on different day): _____
- Post day 42 follow-up healing assessment (specify days since device placement): _____
- Unscheduled visit (specify days since device placement): _____

Is there a photographer present to take pictures of the procedure (circle one): Yes No

(If 'No,' do not proceed until a photographer is available. Photos must be taken with the photo frame, including client ID number, date and pain score before and after device removal).

Has there been a change to the client's medication since device placement (circle one): Yes No

(If 'Yes,' please record the medication on the medications CRF page).

Summary of Follow-Up:

Clinical course leading to client's visit today: _____

Care/advice provided:

Medication given (circle one)? Yes No

If yes, drug (name, dose and total quantity dispensed):

For removal visit, was anesthesia required during removal (circle one): Yes No NA (not removal visit)

If "Yes," what? _____

For removal visit, were there any device-related events or AEs that occurred during the removal (circle one):

Yes No NA (Device not removed this visit)

If "Yes," please record on Adverse Events form.

For removal visit, provider evaluation from 1 to 10 (1 being worst): _____

Name of provider who removed the ShangRing device: _____

Healing status observed by clinician (select one): Healed Not Healed NA (pre-day 42 visit)

Clinical healing defined as: clinical healing after MC by any method is intact epithelium (unbroken skin) covering the wound as judged by the provider on visual inspection, meaning that none of the following are present: sutures, scabbing, drainage, moisture, gaps between epithelial edges or ulceration.

Was client instructed not to masturbate until completely healed (select one)? Yes No NA (client healed)

Was client reminded to abstain from sexual intercourse until completely healed (select one)?

Yes No NA (client healed)

Was client reminded to return to the site in the event of any unexpected situation, in case of pain, or if client has not yet had ring removed, if ring is displaced (select one)? Yes No

Adverse Events

Was there an Adverse Event seen/reported during follow-up (select one): Yes No

If yes, how would you rate the AE (circle one, refer to definitions below): Mild Moderate Severe

Severity cannot be classified (if problem with placement)

Adverse Event Definitions:

Mild: classification indicates minimal or no intervention is required beyond reassurance and observation

Moderate: classification relates to those AEs that are neither mild nor severe, require intervention, and are usually managed on site

Severe: classification requires extensive intervention with referral or specialist input

NB: If any Moderate, Severe, or Severity not classified adverse events above are checked, complete the AE form.

For unscheduled visits, has the client experienced a device-related event or AE since his last visit (select one):

Yes No NA (not an unscheduled visit)

For unscheduled visits, please describe the reason for the unscheduled visit: _____

Is circumcision progressing as expected (select one)? Yes No

If "No," please explain: _____

Assessment (Before Discharge)

Clinical disposition and AE management: _____

Next visit date, if applicable (dd-mm-yyyy): _____

Discharged by (Full name and surname): _____

Signature: _____

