Evaluation Goal:

To evaluate the safety and acceptability of the ShangRing device for nonsurgical circumcision in routine clinical settings, as a part of a comprehensive HIV prevention program for males in VMMC programs.

Evaluation Endpoints:

Primary Endpoint: the proportion of males experiencing mild, moderate and severe adverse events (AEs) associated with ShangRing circumcision procedures, including both intra- and post-operative events, and all device-related malfunctions (e.g., early spontaneous detachment).

Secondary Endpoints:

- Training needed for proficiency using the ShangRing device, including number of procedures to become fully proficient at applying and removing the ShangRing device.
- Client and provider acceptability, client satisfaction, and duration of procedure.
- The percentage of clients clinically healed 49-52 days post-placement of the ShangRing device, and the time at which point all clients are clinically healed.

Evaluation Design

Training Phase: this phase will be used to evaluate the training requirements for implementation by mid-level providers, to preliminarily assess acceptability to providers, and to monitor logistical needs. Each clinician will perform no fewer than 10 ShangRing device placements, and 5 ShangRing removals before start of the next phase (implementation pilot).

Implementation Pilot: following the training period, 575 male clients will be recruited to undergo circumcision with the ShangRing device in the context of routine service delivery.

Data will be collected at up to at least 5 points in time: at enrollment and device placement (day 0), at device removal (day 7), during a follow-up phone call (day 10), in-depth qualitative interviews for 50 purposefully selected clients (day 28), at an in-person follow-up visit to assess wound healing (day 49), and at subsequent weekly visits to assess healing for those not completely healed at day 49.

Upon completion of the implementation pilot, the data will be analyzed and used to assist with policy decisions and recommendations on ShangRing use in adult male circumcision programs.

Section C: Protocol

Introduction

Voluntary Male Medical Circumcision (VMMC), VMMC Devices and ShangRing

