 - Total number of clients who fail to return to the circumcision site (or site indicated by service providers) for recommended follow-up (whether removal visit or AE follow-up).
 - Proportion of all men receiving VMMC services at the evaluation sites who choose ShangRing method instead of surgical circumcision.
- Document provider acceptability of ShangRing, to be measured by the following:
 - Provider perceived ease of application, ease of removal, ease of clinical management of adverse events, and preferences in comparison to conventional circumcision methods.
- Document duration of procedures, and problems encountered during procedures and post-procedure care, to be measured by the following:
 - ShangRing application time will be measured, including the overall time the client is on the procedure table, and the time required for discreet application activities: client preparation time (including application of local anesthetic and sizing), marking and device application, and clean-up time.
 - ShangRing removal time will be measured, including the overall time the client is on the procedure table, the time required for discreet removal activities, and time for post removal instructions given to the client.
- The percentage of clients determined by a clinician to be clinically healed 49-52 days post-placement of the ShangRing device (42 days post-removal), and the time at which point all clients are clinically healed.
 - Healing will be documented by evaluation staff, who will take photographs of the client's genital area during the follow-up visits.
 - Healing will meet the definition of clinical healing after VMMC, defined as:
 - "Intact epithelium (unbroken skin) covering the wound as judged by the provider on visual inspection, meaning that none of the following are present: sutures, scabbing, drainage, moisture, gaps between epithelial edges or ulceration."²⁵

Evaluation Design

Overall Design

This implementation pilot is comprised of two phases: a training phase and the main implementation pilot. During the training phase clinicians at the participating sites will be trained in the use of the ShangRing device. Upon completion of the training phase, the main implementation pilot will begin. The implementation pilot is a single arm, open label, prospective cohort evaluation.

Description of Evaluation Populations and Catchment Areas

Shinyanga, Tanzania

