Potential clients will receive a medical history screening and a genital examination conducted by the VMMC provider to determine that they are in overall good physical health. Additional inclusion criteria include the following:

- Male aged 13 years and older
- Uncircumcised following physical assessment
- Seeking medical circumcision at one of the evaluation sites

- Consents to an HIV test.
- Agrees to be circumcised using the ShangRing device
 - Those aged 13-17 years will also require parental/guardian approval in order to be included in addition to providing assent. Parents must also agree to be present at the facility during the circumcision (though not in the operating room unless requested by the client), for the discharge instructions, and for subsequent follow-up visits.
- Penis fits into one of the 18 ShangRing ring sizes
- Able to understand the evaluation procedures and requirements
- Agrees to abstain from sexual intercourse and masturbation, for six (6) weeks post removal, seven (7) weeks total
- Lives within 30 kilometers of the facility in Shinyanga, Tanzania
- Willing to provide valid contact information (i.e. telephone number, address of residence, place of employment and other locator information) and willing to receive communications and/or follow-up visits, clients may also be asked for names of relatives or friends to be contacted in the event that the client cannot be reached
- Has an activated cell/mobile phone or access to a cell/mobile phone
- Agrees to return for a follow-up visit to assess healing day 49 post-placement (42 days post-removal).
- If not healed at the day 49 post-placement visit, agrees to return for weekly follow up visits until healed.
- Agrees to a 10 day post-placement (3 days post-removal) telephone call to assess and detect symptoms of AEs
- Able to communicate in English and/or Swahili
- Capable and willing to provide written informed consent (18 years and older), or written informed consent from a parent guardian (13-17 years) to participate for both HTS and VMMC services.

Client Exclusion Criteria

Clients who do not meet the inclusion criteria above and who have the following known medical conditions will be excluded from the evaluation:

- Cognitive impairment that prevents the client from providing consent

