The primary focus of the healing component is to determine the percentage of men that are clinically healed by day 49-52 following the placement of the ShangRing device (42-45 days post-removal), and to determine the time point post-placement at which all clients are clinically healed. All clients will be asked to return for a day-49 healing assessment, where a provider will review the clients wound to determine healing. As noted above, the wound will be considered healed if it meets the clinical definition of healing after VMMC, and will be indicated as such on the CRF. All clients will also have a photograph of their genital area taken at this visit to document healing. If the client is not clinically healed at the day-49 healing assessment, the client will be asked to return for another assessment in one week's time. Weekly healing assessments will continue until all clients are clinically healed.

Table 2: Implementation Pilot: Training and Implementation Phases

Evaluation Component	Sample Size	Endpoints	Methods and Data Collection
Phase 1: Training	Approximately 80-120, depending upon # of providers trained (at least 10 clients per provider)	
Primary endpoints:
 
 - Provider training needs - Provider acceptability 
Secondary endpoints:
 
 - Procedure and removal times 
Training Needs Component
 
Primary endpoints:
 
 - Provider proficiency with applying and removing the device 
Secondary endpoints:
 
 - Adverse events and device-related incidents - Procedure and removal times - Training satisfaction and needs of providers 	
Administered knowledge and theory based tests
 
Supervisor/doctor observation
 
Standardized forms to collect data on adverse events and device-related adverse events
 
Client records
 
Qualitative interview with providers
 
Photographs of the client's genital area, to be taken post-device removal (day 7), and at the day 49 healing assessment visit and at subsequent weekly healing visits

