Phase 2: Implementation Cohort Evaluation	455-495 (Depending upon # performed during training phase)	
Safety Component
 
Primary endpoints:
 
 - Adverse events and device-related incidents 
Secondary endpoints:
 
 - Safety of procedure/removal - Provider perception of technical difficulty and complications during procedure and removal process 
Provider Acceptability Component:
 
 - Provider acceptability - Practicality of device use - Procedure and removal times 
Client Acceptability Component:
 
 - Client satisfaction - Cosmetic results - Comfort: 
 - During procedure to place device - During (nocturnal) erections - During removal 
Healing Component
 
 - Percentage of men clinically healed 49-52 days post placement (42 days post-removal) - Time at which point all men are clinically healed 	
Standardized forms to collect data on adverse events and device-related adverse events
 
Client records
 
Brief surveys to collect data on reasons to decline participation in the evaluation as indirect measure of acceptability
 
Brief surveys to collect data on client experience with the ShangRing as an indirect measure of acceptability
 
Qualitative interview with providers
 
Qualitative interviews with 50 male clients
 
Qualitative interview with providers
 
Brief surveys to collect data on reasons to decline participation in the evaluation as indirect measure of acceptability
 
Client records – including those recording application and removal times
 
Client records indicating healing per VMMC healing definition as completed by providers during day 49 healing assessment visit and subsequent weekly healing visits for those not healed at day 49
 
Photographs of the client's genital area, to be taken post-device removal (day 7), and at the day 49 healing assessment visit and at subsequent weekly healing visits

Evaluation Procedures and Logistics

Evaluation Offices

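### The rule that makes a client lost to follow-up if he misses day 49 conflicts with a healing endpoint window that runs to day 52, and the follow-up form misdates the same visit as day 42 post-placement.

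*Protocol*

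**What the plan says.** **The endpoint window.** The Executive Summary lists as a secondary endpoint "The percentage of clients clinically healed 49-52 days post-placement of the ShangRing device". The main Secondary Endpoints section repeats it as "clinically healed 49-52 days post-placement of the ShangRing device (42 days post-removal", and Table 2 has "Percentage of men clinically healed 49-52 days post placement (42 days post-removal". The Healing Component section gives the window on both clocks: "clinically healed by day 49-52 following the placement of the ShangRing device (42-45 days post-removal". A second part of the same endpoint is the time by which all clients are healed, which has no upper day.

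**The visit.** The inclusion criteria require that the client "Agrees to return for a follow-up visit to assess healing day 49 post-placement (42 days post-removal". The follow-up schedule, the counselling text and the data-collection list use the same day.

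**The loss rule.** Follow-Up Visits sends a reminder text on day 42 and a second on day 45 if the appointment is unconfirmed, then calls daily on days 47 to 49. A client who does not attend on day 49, and has not signalled withdrawal, is then classed as lost to follow-up. No grace days are given. The same section says that missed visits other than the day-7 visit are pursued by text or call. The telephone script in Appendix XIII offers a client another time for a missed appointment.

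**The analysis.** The Analysis Overview reports the percentage healed by day 49, not over days 49-52. It also reports the number and percentage who do not complete the evaluation.

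**The form.** Appendix XII is used for every follow-up visit. Its visit types include "Day 42 post-placement healing assessment (specify day if client comes in on different day" and "Post day 42 follow-up healing assessment (specify days since device placement", and its healing-status item offers "Healed Not Healed NA (pre-day 42 visit".

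**The concern.** The loss rule closes the healing visit on the first day of the window in which the endpoint is to be assessed. A site that follows it literally records a client as lost on the evening of day 49. If the client then answers a call, comes in on day 51 and is examined, the site has an in-window healing result for a man whose disposition is already lost. Nothing in the protocol says that the status is withdrawn or which record prevails, and two sites could resolve it differently.

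What is at stake is the disposition record and the consistency of the healing endpoint's definition. The Analysis Overview adds a third version of the timing: a man first examined on day 51 can be counted as healed within 49-52, but his form cannot show that he was healed by day 49.

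The form label is a separate and lesser matter. Staff must select one visit type. A first healing visit held exactly on schedule, on day 49, is by the printed wording both a different day from the labelled visit and a visit after day 42. Some staff may tick the first box and some the second.

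**Working it through.** **Inputs**

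| Item | Value | Place in the protocol |
|---|---|---|
| Device removal | day 7 post-placement | Executive Summary, Evaluation Design |
| Healing visit | day 49 post-placement, 42 days post-removal | Client Inclusion Criteria; Follow-Up Visits |
| Endpoint window | days 49-52 post-placement, 42-45 post-removal | Healing Component |
| Check-in call | day 10, with the healing visit 39 days later | Follow-Up Visits; Appendix XIV |
| Loss rule | not attending on day 49 | Follow-Up Visits |
| Form label | day 42 post-placement | Appendix XII |
| Sample size | 575 | Sample Size section |

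**Step 1. Reproduce the protocol's own dates.** With removal on day 7:
- 7 + 42 = 49, the planned visit.
- 7 + 45 = 52, the end of the window.
- 10 + 39 = 49, so the check-in call form agrees with the body.

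The four-day window is therefore spelled out consistently on both clocks in the Healing Component. The Secondary Endpoints section and Table 2 show only the first day (42) on the post-removal clock.

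**Step 2. Set the loss rule against the window.** The window days are 49, 50, 51 and 52. The rule has already applied on days 50, 51 and 52, which is 3 of 4. If loss were declared only after day 52, the number would be 0 of 4.

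**Step 3. Effect on reported figures.**
- Percentage healed: 0 points, if men examined on days 50-52 are analysed as observed. No section removes them.
- Non-completion: if the day-49 status is what gets counted, k clients seen on days 50-52 add k/575. For one client, 1/575 = 0.17%. The protocol gives no value or basis for k.

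**Step 4. The form label.** Day 42 post-placement is 42 - 7 = 35 days post-removal. The planned visit is 49 - 42 = 7 days later. The number 42 is correct on the post-removal clock and has been printed with a post-placement label. In Follow-Up Visits, day 42 post-placement is the day of the reminder text. The same form records the placement date, the visit date and the actual day, so days since placement = visit date - placement date can always be computed.

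**The case against.** The best case on the other side has four parts.

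1. *The form label does no harm.* Every text that books or announces the visit says day 49, and the form's own dates give the true day. This stands: the label is an editorial slip that affects visit-type coding and nothing else. A reader might infer that men would be called in, or their healing judged, a week early. The documents do not support that.

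2. *The loss status may never reach an analysis.* The Analysis Overview does not tie non-completion to the day-49 rule, nothing forbids updating a status when the client attends, and the final handling of dispositions can be left to an analysis plan. This also largely stands, so overstatement of non-completion is conditional. It does not remove the conflict, because the rule is a conduct instruction in the protocol and sites apply it before any analysis plan does.

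3. *Three of four sounds larger than it is.* The fraction counts calendar days, not clients. Visits are booked for day 49 and preceded by reminders, so most attendance may fall there. It would be wrong to read it as three quarters of clients.

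4. *A bare day-52 cut-off only moves the problem.* A man first seen after day 52 would be lost while still contributing to the time at which all clients are healed. This is right, and the fix has to allow the status to be reversed.

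Two further inferences should be resisted. One is that men seen on days 50-52 are dropped from the healing percentage, which would bias it; no section says so. The other is that the day-49 loss removes men from the adverse-event rate. The section on clients lost to follow-up excludes only those who do not return for device removal.

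**Conclusion.** The inconsistency is real and modest. Taken literally, the day-49 rule assigns lost status on 3 of the 4 days of the endpoint window, while other sections provide for contacting and rescheduling men who miss a visit. The protocol does not say which status governs. The percentage healed is unaffected provided examined men are analysed as observed. The non-completion count is affected only if the day-49 status feeds it, and the number of clients involved is unknown. The form mislabels the visit by 7 days in a way that can be repaired from recorded dates. The primary endpoint and the sample size do not depend on any of this.

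The post-removal day counts assume removal on day 7 as scheduled, and the 0.17% assumes a denominator of 575. The point merits correction because sites act on the rule and the form during conduct, and the repair is simple.

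**What to change.** - **Follow-Up Visits:** assign lost-to-follow-up for the healing visit only after day 52. Continue the existing text and telephone follow-up until then. State that the status is reversed if the client attends later, so that he still contributes to the time at which all clients are healed.
- **Appendix XII:** relabel the three items as the day 49 (window 49-52) post-placement healing assessment, the post-day-49 follow-up assessment, and not applicable before day 49 post-placement.
- **Endpoint assignment:** place visits in the 49-52 window from the recorded placement and visit dates, whichever visit type is ticked.
- **Analysis Overview:** replace the reference to healing by day 49 with the 49-52 window used in the endpoint definition.

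The cost is one form correction, short wording changes in two sections, a sentence on assigning visits by date, and a few more calls or texts to men who miss day 49. No new data items are needed.
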